**LIST OF ABBREVIATIONS AND DEFINITIONS OF TERMS**

Abbreviation	Definition
AAV	adeno-associated virus
AE	adverse event
AESI	adverse event of special interest
aHUS	atypical hemolytic uremic syndrome
ALT	alanine aminotransferase
AST	aspartate aminotransferase
CFR	Code of Federal Regulations
CCI	CCI [REDACTED]
CRF	case report form
CRO	Contract research organization
DMC	data monitoring committee
DMD	Duchenne muscular dystrophy
CCI	CCI [REDACTED]
ECG	electrocardiogram
ECHO	echocardiogram
GCP	Good Clinical Practices
GGT	gamma-glutamyl transferase
GLDH	glutamate dehydrogenase
HIV	human immunodeficiency virus
ICF	informed consent form
ICH	International Council on Harmonisation
IEC	Independent Ethics Committee

Abbreviation	Definition
IF	immunofluorescence
IP	investigational product
IRB	Institutional Review Board
ITT	intent-to-treat
IV	intravenous(ly)
IXRS	interactive voice/web response system
CCI	CCI [REDACTED]
NOAEL	no observable adverse effect level
NSAA	North Star Ambulatory Assessment
PCS	potentially clinically significant
PDPF	percent dystrophin positive fibers
PI	Principal Investigator
CCI	CCI [REDACTED]
qPCR	quantitative polymerase chain reaction
CCI	CCI [REDACTED]
SAE	serious adverse event
SAP	Statistical Analysis Plan
SoA	Schedule of Activities
SUSARs	suspected unexpected serious adverse reactions
TEAE	treatment-emergent adverse event
ULN	upper limit of normal
WBC	white blood cell

## 1. PROTOCOL SUMMARY

### 1.1. Synopsis

**Protocol Title:** A Multicenter, Randomized, Double-Blind, Placebo-Controlled Trial for Duchenne Muscular Dystrophy Using SRP-9001

**Short Title:** A Randomized, Double-Blind, Placebo-Controlled Study of SRP-9001 for Duchenne Muscular Dystrophy

[figure not shown]
**Rationale:** Based on nonclinical studies in mice and canine species deficient in dystrophin and from the 2006 Duchenne muscular dystrophy (DMD) trial ([Mendell 2010](#)) and the ongoing microDys-IV-001 clinical trial, data supports the use of gene transfer for micro-dystrophin expression in skeletal and cardiac muscle.

**Objectives and Endpoints:** This study will assess the safety and efficacy of exogenous gene transfer in DMD patients by measuring biological and clinical endpoints in 3 parts: two 48-week randomized, double-blinded, placebo-controlled periods (Part 1 and 2), and an open-label follow-up period (Part 3). The primary objectives of this study are the assessments of the safety and efficacy of intravenous (IV) administration of SRP-9001 in DMD patients.

[figure not shown]
Objectives	Endpoints
Safety	

To evaluate the safety of SRP-9001

	

Treatment-emergent adverse events (TEAEs) and serious adverse events (SAEs)

Select clinical laboratory assessments

Primary	

To evaluate micro-dystrophin expression from SRP-9001 at 12 weeks post dosing (Part 1) as measured by Western blot of biopsied muscle tissue

	

Change in quantity of micro-dystrophin protein expression from Baseline to Week 12 (Part 1) as measured by Western blot

To evaluate the effect of SRP-9001 on physical functional assessments as assessed by the North Star Ambulatory Assessment (NSAA) over 48 weeks (Part 1)

	

Change in NSAA total score from Baseline to Week 48 (Part 1)

Objectives	Endpoints
Secondary	


• To evaluate the effect of SRP-9001 on physical functional assessments over 48 weeks (Part 1)

	

• Change in time to rise from the floor from Baseline to Week 48 (Part 1)

• Change in time to ascend 4 steps from Baseline to Week 48 (Part 1)

• Change in time of 10-meter timed test from Baseline to Week 48 (Part 1)

• Change in time of 100-meter timed test from Baseline to Week 48 (Part 1)

• To evaluate micro-dystrophin expression from SRP-9001 at 12 weeks (Part 1) as measured by immunofluorescence (IF) fiber intensity of biopsied muscle tissue

• To evaluate micro-dystrophin expression from SRP-9001 at 12 weeks (Part 1) as measured by IF percent dystrophin positive fibers (PDPF) of biopsied muscle tissue

	

• Change in micro-dystrophin expression from Baseline to Week 12 (Part 1) as measured by IF fiber intensity

• Change in micro-dystrophin expression from Baseline to Week 12 (Part 1) as measured by IF PDPF

[figure not shown]
CCI

[figure not shown]
CCI

CCI

[figure not shown]

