##### **3.1.2. Treatment Period**

###### **3.1.2.1. Part 1**

Part 1 is a 48-week randomized, double-blind, placebo-controlled period. Patients meeting eligibility requirements will be randomized prior to or on Day -1 to SRP-9001 or placebo in a 1:1 ratio by IXRS. Up to 22 patients will receive IV SRP-9001 ( $1.33 \times 10^{14}$  vg/kg) and up to

22 patients will receive a matching volume (up to 10 mL/kg) of placebo (lactated Ringer's solution).

Patients may be admitted to the hospital the day before the study treatment is infused at the discretion of the Investigator. On Day -1, the patient will receive a physical examination, have vital signs collected, and provide blood and urine samples.

The day prior to the study treatment infusion (SRP-9001 or placebo), patient's background dose of steroid for DMD will be increased to at least 1 mg/kg of a glucocorticoid (prednisone equivalent) daily and continue at this level for at least 60 days after the infusion unless earlier tapering is judged by the PI to be in the best interest of the patient.

SRP-9001 or placebo will be administered IV on Day 1 over 1 to 2 hours. Vital signs will be monitored during and after the infusion according to the Study Operations Manual.

On the day after the infusion (Day 2), patients will receive a physical examination, have vital signs collected, and provide blood and urine samples before being discharged or in clinic, as applicable.

Patients will be followed for 48 weeks in Part 1. Patients will complete clinic follow-up visits at the following time points: **cci** relative to the infusion on Day 1). In addition, at **cci**, patients will complete follow-up visits for assessment of liver function tests. If the **cci** visits occur in the clinic, a blood sample for the assessment of glutamate dehydrogenase (GLDH) will be collected.

All patients will have a muscle biopsy performed at Week 12 in Part 1. **cci**

All patients, parents, caregivers, the Examining Team, the Treating Team, physiotherapists, and clinical staff will be blinded to the treatment the patient receives (SRP-9001 or placebo). The study will be unblinded when the last patient completes the **cci** visit. Refer to the study unblinding plan for additional details.

Safety will be assessed by monitoring of treatment-emergent adverse events (TEAEs), serious adverse events (SAEs), and select laboratory assessments.

Refer to Section 6 Study Assessments and Procedures for additional information.

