### 4.1. Inclusion Criteria

Participants are eligible to be included in the study only if all of the following criteria apply:

1. Male, 4 to 7 years of age, inclusive, at the time of screening in Part 1.
2. Molecular characterization of the DMD gene with either frameshift (deletion or duplication) between exons 18 to 58, or premature stop codon mutation between exons 18 to 58.
3. Indication of symptomatic muscular dystrophy:  
[REDACTED]  
[REDACTED]
4. Ability to cooperate with motor assessment testing.
5. Stable dose equivalent of oral corticosteroids for at least 12 weeks before screening and the dose is expected to remain constant (except for potential modifications to accommodate changes in weight) throughout Part 1 and 2 of the study.

[figure not shown]

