### **6.1.5. Physical Functional Assessments**

Efficacy will be measured by the following functional tests: time to rise from the floor, ascend 4 steps, NSAA, 10-meter timed test, and 100-meter timed test. Assessments will be administered by a physiotherapist. The physiotherapist will not have access to information that can disclose study treatment, laboratory results, or adverse events.

The patient's functional assessments will be videotaped for quality control and may be viewed by government agencies if the study goes through a quality review. These videos may also be used to demonstrate any functional outcomes related to the study drug and shared at scientific meetings and/or with regulatory authorities.

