#### **6.1.5.1. Time to Rise from the Floor**

This assessment is performed as a part of the NSAA. It measures the time taken to rise from supine to standing.

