#### **6.1.5.3. North Star Ambulatory Assessment**

The NSAA is a healthcare provider administered scale that rates patient performance on various functional activities ([Mazzone 2010](#)). During this assessment, patients will be asked to perform 17 different functional activities, including a 10-meter walk/run, rising from a sitting position to standing position, standing on 1 leg, climbing a box step, descending a box step, rising from lying to sitting, rising from the floor, while supine lifting head off floor, standing on heels, and jumping.

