#### **6.1.5.5. 100-meter Timed Test**

This assessment measures the time needed to move 100 meters.

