## 7.4. Statistical Analyses

An SAP will be developed and finalized before database lock and unblinding of the study data. It will describe the details of the statistical analyses. This section is a summary of the planned statistical analyses of the primary and secondary endpoints as well as the safety analyses.

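### Does the protocol need a rule for a boy who attempts a timed test but cannot finish it?

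*Combined protocol and SAP*

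**What the plan says.** Section 1.1 lists four functional secondary endpoints, each a change in time from Baseline to Week 48 of Part 1: rise from the floor ("Change in time to rise from the floor from Baseline to Week 48 (Part 1"), ascend 4 steps, 10 meters and 100 meters. Sections 6.1.5.1, 6.1.5.2, 6.1.5.4 and 6.1.5.5 describe the tests in a line or two each, for instance "This assessment measures the time needed to move 100 meters". No time limit is given, and no value for an attempt that fails.

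Other parts of the plan bear on the point:

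- On the rise test, Section 6.1.5.1 says "This assessment is performed as a part of the NSAA". Section 6.1.5.3 calls the NSAA a "scale that rates patient performance on various functional activities" and lists rising from the floor and the 10-meter walk/run among those activities.
- Section 6.1.5 says the "functional assessments will be videotaped for quality control".
- Section 4.1 requires "Ability to cooperate with motor assessment testing"; criterion 3, on symptomatic disease, is redacted.
- Section 3.1.2.1 sets the arm size: "Up to 22 patients will receive IV SRP-9001", and the same maximum for placebo.
- Section 7.4 states "An SAP will be developed and finalized before database lock and unblinding of the study data". Section 7.4.1 says secondary endpoints are analysed by methods similar to the primary ones, with details in the SAP. Section 9.1.5.1 refers to CRF Completion Guidelines.

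**The concern.** A rating scale can grade a failed attempt; a stopwatch cannot. Section 2.2 describes a relentlessly progressive disease, so a boy could lose a test during the 48 weeks. His result could then be treated as missing, ranked worst, converted to a velocity of zero, or set to a cap. Each is defensible, and in arms of 22 they need not agree.

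There is also a recording question. Whether a boy tried and failed or simply was not tested is known at the visit, whereas the SAP need only exist before lock and unblinding. If the reason for a missing time were not captured, a mixed model would by default treat an inability as missing at random. At stake are the estimates and significance of four secondary endpoints. The primary NSAA endpoint is not affected.

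**Working it through.** **Inputs.** From the protocol: at most 22 per arm and a 2-sided 0.05 level. The visible text gives no inability rate, SD of timed-test change or cap, and the assumptions behind the sample size are redacted, so the planned power cannot be reproduced. Everything else below is assumed.

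**1. Weight of one boy.** Assume a 7 s baseline. A 30 s cap adds (30 − 7)/22 = 1.05 s to his arm's mean change. A 15 s cap adds (15 − 7)/22 = 0.36 s. Left missing, he adds nothing.

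**2. Idealised test in SD units.** The difference detectable with 80% power is (1.960 + 0.842) × √(2/22) = 0.845 SD. Suppose one boy per arm is unable.

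- Both missing (21 v 21): t = 0.845/√(2/21) = 2.74, p = 0.009.
- Both assigned 5 SDs of worsening: the difference barely moves, 0.845 × 21/22 = 0.807. The variance does. Placebo: [20 + (21/22) × 5²]/21 = 2.09. SRP-9001: [20 + (21/22) × 5.845²]/21 = 2.51. Pooled SD = √2.30 = 1.52, so t = 0.807/(1.52 × 0.3015) = 1.76, p = 0.085.
- The same steps give p = 0.020 at 2 SDs, 0.034 at 3 and 0.28 at 10. A rank test gives 0.020 whatever value is assigned, against 0.013 with both boys excluded.

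So with one boy in each arm the harm is variance inflation from an extreme assigned value. Mild values and ranks leave the verdict unchanged here.

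**3. Simulation of rise time.** There were 1,500 runs per scenario (Monte Carlo error about ±2.4 points) and 22 boys per arm. Assumed: baseline median 4.5 s with log SD 0.35; 48-week log change +0.15 with SD 0.25; treatment effect −0.25 on the log scale (about −1.27 s); visit error SD 0.12; visits at Weeks 12, 24, 36 and 48. Missing values were multiply imputed from baseline and earlier visits, followed by ANCOVA.

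*(a) The slowest boys in an arm are declared unable, in fixed numbers.* Power:

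| Unable, placebo / SRP-9001 | Missing | Worst rank | Velocity 0 | 15 s cap | 30 s cap |
|---|---|---|---|---|---|
| 0 / 0 | 69% | 71% | 71% | 69% | 69% |
| 1 / 1 | 73% | 67% | 65% | 38% | 2% |
| 1 / 0 | 68% | 74% | 72% | 72% | 43% |
| 0 / 1 | 75% | 66% | 58% | 34% | 1% |
| 1 / 2 | 74% | 57% | 47% | 12% | 0.3% |

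*(b) A boy is unable when his time passes a limit common to both arms.* Power, with the last column comparing the missing-at-random estimate with the true effect:

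| Limit | Unable, placebo / SRP-9001 | Missing | Velocity 0 | Worst rank | Cap at limit | Estimate v true |
|---|---|---|---|---|---|---|
| 10 s | 8.8% / 3.6% | 68.6% | 68.9% | 69.3% | 71.1% | −1.10 v −1.27 s |
| 12 s | 3.7% / 1.2% | 69.1% | 70.3% | 70.2% | 69.9% | −1.18 v −1.28 s |
| 15 s | 1.1% / 0.2% | 72.6% | 70.6% | 73.6% | 72.4% | −1.26 v −1.30 s |

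The widest spread between rules is 73.6 − 70.6 = 3.0 points. The missing-at-random estimate is too small by 13%, 8% and 3%. Rejection under the null is 3.7% to 5.4% across rules.

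**4. Reading (a) against (b).** At the 10 s limit about 0.088 × 22 = 1.9 placebo boys and 0.036 × 22 = 0.8 SRP-9001 boys are unable. That is more in total than one per arm, yet the rules agree. The large losses in (a) have two sources. One is the cap: 30 s is 30/4.5 = 6.7 times the assumed median. The other is how the counts are forced. In a re-run of 3,000 trials, in 80% of the 0/1 trials at least one placebo boy slower than the unable SRP-9001 boy still completed the test; in 1/1 the share was 58%. Without fixed caps, the 1/1 range is 65% to 73% and the 1/0 range 68% to 74%.

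**The case for a change.** The best argument for a change is that deferral to the SAP does not settle recording. A SAP can only use what the sites wrote down. Section 7.5.1 also allows some personnel to be unblinded to Week 12 expression data, where Section 7.2 expects a dramatic difference, before the Part 1 analysis. A sentence in Section 6.1.5 separating attempted-but-unable from not done would cost almost nothing.

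Part of this stands. The visible text does not show that the distinction is recorded, and a SAP ought to name its rule. But the usual home for such a code is the CRF and its guidelines, which cannot be judged unseen. The information is not lost either: functional assessments are filmed, and the rise and 10-meter tasks are also rated within the NSAA. For the 4-step and 100-meter tests the video is the only visible back-up. On timing, Section 7.4 already puts the SAP before unblinding, and Section 7.5.1 requires a procedure to keep the study double-blind after the Week 12 look.

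It is also true that an excess of unable boys on SRP-9001 separates even the rules without a cap: 47% to 74% power in the 1/2 case. That is a reason for the SAP to choose deliberately. It does not show that the protocol is wrong, since several choices are acceptable and the protocol favours none.

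**Conclusion.** No change to the plan. Section 6.1.5 is silent on uncompleted attempts, but this is detail the protocol leaves to the SAP and the CRF guidelines, and analysts ordinarily supply it there. Nothing shows that either lacks it. A colleague who holds both can confirm in minutes that unable is coded apart from not done, and that one rule per test, with a sensitivity analysis, was fixed before Part 1 unblinding.

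The likely size is small: at most 3 points of power between rules under a common limit, an estimate 3% to 13% too small if such boys are treated as missing at random, and no type I inflation. Powers of 1% to 2% require a 30 s cap that no section mentions. These figures rest on one set of assumed inputs for rise time. They do not carry over to the 100-meter test, and arms smaller than 22 would be more sensitive. Only secondary endpoints are involved.

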## 1.2. Schema

[figure not shown]
D = day; CCl WK = week.

CCl

[figure not shown]
CCI

CCI

[figure not shown]
CCI

CCI

CCI

## **2. INTRODUCTION**

SRP-9001 is a nonreplicating, recombinant adeno-associated virus (AAV) that is being developed for treatment in patients with Duchenne muscular dystrophy (DMD).

### **2.1. Study Rationale**

There is a strong rationale for systemic gene delivery in young DMD boys based on studies of the natural history of this disease. Gene replacement therapy has been studied for the past 10 to 15 years and shows very favorable results in nonclinical studies in mice and canine species deficient in dystrophin.

The goal of SRP-9001 therapy is to increase the expression level of the micro-dystrophin protein in skeletal and cardiac muscle in order to increase strength and protect from contraction-induced injury. Correction of the underlying genetic defect in DMD using gene replacement with SRP-9001 is the most promising treatment. Duchenne muscular dystrophy affects all skeletal muscles in the body, in addition to the diaphragm and heart. As such, a systemic approach is necessary in order to provide the best possible prospect of direct benefit to patients. Utilizing the rAAVrh74 serotype allows for efficient transduction of cardiac, skeletal, and diaphragm muscle without the increased risk of regional delivery strategies. Increased dystrophin expression *in vivo* may potentially improve patient's muscle function. SRP-9001 appears to have a favorable safety profile and to be generally well-tolerated in nonclinical studies.

All patients will be screened for pre-existing immunity to rAAVrh74 to avoid potential immune reaction and rejection following transfer of the gene.

### **2.2. Background**

Duchenne muscular dystrophy is the most common, severe childhood form of muscular dystrophy. Inheritance follows an X-linked recessive pattern. Birth prevalence has been estimated at 1 in 3500 to 5000 live male births ([Mendell 2010](#)). Approximately one-third of cases represent new mutations of the DMD gene with the remaining inherited on the X chromosome from a carrier mother. Questions usually begin to surface between 3 to 5 years of age regarding reduced motor skills that alert a need for diagnostic evaluation. Earlier recognition results from delay in motor milestones or family history. At times aminotransaminases are found to be elevated that lead to detection of creatine kinase (CK) elevation and subsequent further testing. Duchenne muscular dystrophy is relentlessly progressive with loss of ambulation by 12 years of age ([Brooke 1983](#)). Historically, patients died from respiratory complications. Now, a variety of factors protect the respiratory system related to improved supportive equipment, antibiotics, vaccines, and other ancillary methods ([Eagle 2002](#)). Consequently, patients tend to live longer but eventually succumb to cardiac failure ([D'Amario 2017](#)).

### **2.3. Benefit/Risk Assessment**

Nonclinical data and results from clinical study SRP-9001-101 suggest a positive benefit/risk relationship and support clinical investigation of SRP-9001 gene replacement in DMD patients.

More detailed information about the known and expected benefits and risks and reasonably expected adverse events (AEs) of SRP-9001 may be found in the Investigator's Brochure.

### **3. STUDY DESIGN**

#### **3.1. Overall Design**

This is a randomized, double-blind, placebo-controlled, 3-part clinical study of systemic gene delivery of SRP-9001 in up to 44 DMD patients 4 to 7 years of age (inclusive) who either have a confirmed frameshift deletion or duplication between exons 18 to 58, or premature stop codon mutation between exons 18 to 58. Patients meeting all eligibility criteria will be randomized to SRP-9001 or placebo by the interactive voice/web response system (IXRS). All patients will have the opportunity to receive intravenous (IV) SRP-9001 ( $1.33 \times 10^{14}$  vg/kg) in either Part 1 or Part 2. Part 3 of the study will be an open-label follow-up period.

The Sponsor has developed a quantitative polymerase chain reaction (qPCR) method using a linear standard for dose titration. This method replaces the previously used qPCR method which used a supercoiled standard for dose titration developed by Nationwide Children's Hospital. The scale for the linear standard method is different from the previous supercoiled standard method. For patients who received a dose in this study based on Nationwide Children's Hospital qPCR method, the dose used was  $2 \times 10^{14}$  vg/kg which corresponds to  $1.33 \times 10^{14}$  vg/kg as measured by the Sponsor's qPCR method using a linear standard. Note that both numbers (ie,  $2 \times 10^{14}$  and  $1.33 \times 10^{14}$  vg/kg) refer to the same quantity of drug given to the patients; only the effective scale for the 2 methods is different. Hence, as of Amendment 5, Version 6, the reassigned dose for the additional patients in the study is  $1.33 \times 10^{14}$  vg/kg, and for the duration of this study, all references to dosing will use  $1.33 \times 10^{14}$  vg/kg.

##### **3.1.1. Screening/Baseline Period**

The Screening/Baseline period will be up to 4 weeks before Day -1 in Part 1. After obtaining informed consent, patients will be evaluated for eligibility. Screening will include collection of demographics and medical history, vital sign measurements, a physical examination, electrocardiogram (ECG), and an echocardiogram (ECHO). Blood and urine samples will be collected for clinical and safety laboratory assessments. Blood samples will also be collected for hepatitis B and C, human immunodeficiency virus (HIV), and antibodies to rAAVrh74 and antigen-specific T-cells to rAAVrh74 capsid and micro-dystrophin. A pretreatment muscle biopsy will involve the gastrocnemius muscle, or a muscle selected by the Principal Investigator (PI) and will be performed after eligibility but before Day -1 in Part 1. The parent/caregiver will be asked to complete questionnaires.

Physical functional assessments will include the time to rise from the floor, time to ascend 4 steps, North Star Ambulatory Assessment (NSAA), the 10-meter timed test, and the 100-meter timed test.

##### **3.1.2. Treatment Period**

###### **3.1.2.1. Part 1**

Part 1 is a 48-week randomized, double-blind, placebo-controlled period. Patients meeting eligibility requirements will be randomized prior to or on Day -1 to SRP-9001 or placebo in a 1:1 ratio by IXRS. Up to 22 patients will receive IV SRP-9001 ( $1.33 \times 10^{14}$  vg/kg) and up to

22 patients will receive a matching volume (up to 10 mL/kg) of placebo (lactated Ringer's solution).

Patients may be admitted to the hospital the day before the study treatment is infused at the discretion of the Investigator. On Day -1, the patient will receive a physical examination, have vital signs collected, and provide blood and urine samples.

The day prior to the study treatment infusion (SRP-9001 or placebo), patient's background dose of steroid for DMD will be increased to at least 1 mg/kg of a glucocorticoid (prednisone equivalent) daily and continue at this level for at least 60 days after the infusion unless earlier tapering is judged by the PI to be in the best interest of the patient.

SRP-9001 or placebo will be administered IV on Day 1 over 1 to 2 hours. Vital signs will be monitored during and after the infusion according to the Study Operations Manual.

On the day after the infusion (Day 2), patients will receive a physical examination, have vital signs collected, and provide blood and urine samples before being discharged or in clinic, as applicable.

Patients will be followed for 48 weeks in Part 1. Patients will complete clinic follow-up visits at the following time points: **cci** relative to the infusion on Day 1). In addition, at **cci**, patients will complete follow-up visits for assessment of liver function tests. If the **cci** visits occur in the clinic, a blood sample for the assessment of glutamate dehydrogenase (GLDH) will be collected.

All patients will have a muscle biopsy performed at Week 12 in Part 1. **cci**

All patients, parents, caregivers, the Examining Team, the Treating Team, physiotherapists, and clinical staff will be blinded to the treatment the patient receives (SRP-9001 or placebo). The study will be unblinded when the last patient completes the **cci** visit. Refer to the study unblinding plan for additional details.

Safety will be assessed by monitoring of treatment-emergent adverse events (TEAEs), serious adverse events (SAEs), and select laboratory assessments.

Refer to Section 6 Study Assessments and Procedures for additional information.

### 3.1.2.2. Part 2

Part 2 of the study will begin after the patient completes Part 1. Patients who were randomized to placebo during Part 1 will receive IV SRP-9001 ( $1.33 \times 10^{14}$  vg/kg) in Part 2. To maintain blinding throughout the study, patients previously randomized and treated with SRP-9001 in Part 1 will receive up to 10 mL/kg placebo (lactated Ringer's solution). Infusions will be given in the same manner as in Part 1.

CCI

- CCI
- CCI
- CCI

Prior to dosing in Part 2, if a patient has rAAVrh74 antibody titers > 1:400, consultation with the unblinded contract research organization (CRO) Medical Director, blinded Sponsor Medical Director, and PI is required prior to dosing. Patients who received placebo in Part 1 and who have rAAVrh74 antibody titers > 1:400 will not be dosed with SRP-9001 nor will they receive a second placebo infusion in Part 2. The patient will be encouraged to continue their follow-up through the last planned visit based on the protocol. If the patient decides to withdraw from the study, they should complete the last planned visit based on the protocol as their final visit.

The day prior to the study treatment (SRP-9001 or placebo) infusion in Part 2, the patient's dose of steroids will be increased to at least 1 mg/kg of a glucocorticoid (prednisone equivalent) daily and continue at this level for at least 60 days after the infusion unless earlier tapering is judged by the PI to be in the best interest of the patient.

CCI

On the day after the infusion, patients will receive a physical examination, have vital signs collected, and provide blood and urine samples before being discharged or in clinic, as applicable. CCI

CCI

Safety will be assessed by monitoring of TEAEs, SAEs, and select laboratory assessments.

Refer to Section 6 Study Assessments and Procedures for additional information.

### 3.1.2.3. Part 3

Part 3 of the study will be an open-label follow-up period. The study will be unblinded once the last patient completes the CCI visit; refer to the study unblinding plan for additional

details. Patients will have the opportunity to complete their 5-year post-infusion follow-up in a long-term extension study. The long-term extension study has been designed to provide a uniform approach to monitoring long-term safety and efficacy in patients who received an infusion of SRP-9001 in a clinical trial.

[figure not shown]
Patients must complete the Week 130 visit at a minimum before rolling over into the long-term extension study. After completion of the Week 130 visit, if patients decide not to continue their follow-up in the long-term extension study, patients will complete an end of study visit.

